4.1.1 Study Duration for Patients

The duration of screening is up to 28 days prior to Cycle 1 Day 1 and the duration of treatment for an individual patient is anticipated to be a median of 3 months. For Parts 2 and 4 only, this will be followed by radiology follow-up visits until disease progression or initiation of new therapy. Upon disease progression or initiation of new therapy, patients enter long term follow-up (every 6 months \pm 1 month) until death, lost to follow-up, withdrawal of consent or study closure, whichever occurs first, for a maximum of 2 years after end of treatment. Long term follow-up visits may occur over the telephone.

The total study duration for an individual patient is estimated to be approximately 12 months.

4.1.2 Number of Patients

Part 1 will enroll up to approximately 50 patients for each of IV Schedule A, IV Schedule B in cohorts of $n \geq 3$ for dose escalation, and up to approximately 12 patients in total for backfill cohorts at certain dose levels and schedules which have been previously cleared by DMC In total, up to approximately 115 patients will be enrolled in Part 1.

Part 2 will enroll up to 30 patients in each cohort, up to a maximum of 60 patients in total. Part 3 will enroll up to 21 patients for each of Schedule A and Schedule B in cohorts of $n \geq 3$ for a maximum of 42 patients in total. Part 4 will enroll up to 30 patients in each cohort, up to a maximum of 90 patients in total.

Combined enrollment for all parts of the study is up to an approximately 310 patients.

4.1.3 Replacement of Patients

In Parts 1 and 3, patients who are unable to be evaluated for toxicity during the DLT window due to discontinuation for unrelated AEs or disease progression will be replaced. In Parts 2 and 4, patients who are withdrawn or removed from treatment or the study will not be replaced.

4.1.4 Number of Sites

Approximately 10 sites in North America and Australia will participate in Parts 1 and 3, and approximately 20 sites in North America and Australia will participate in Parts 2 and 4 of this

global study. During the conduct of the study, additional sites and countries within these regions may be added as necessary.

4.2 Scientific Rationale for Study Design

Aldesleukin is a recombinant human IL-2 protein that has monotherapeutic efficacy in malignant melanoma and RCC. It activates T-cell-mediated tumor inhibition by heterodimerizing the beta and gamma subunits of the IL-2 receptor, leading to phosphorylation of STAT5. However, serious toxicity has limited the clinical utility of IL-2.²⁶ The cause of this toxicity is related to its high binding affinity for CD25⁺ cells: preferential activation of CD25⁺ cells, such as endothelial cells and regulatory T-cells, leads to vascular leak and immunosuppression.^{27,28} NL-201 is a novel immunotherapeutic based on a de novo designed mimic of IL-2 that acts through the same mechanism of action as IL-2 but has no affinity for CD25. The parental protein of NL-201 binds with high affinity and in the correct orientation to the beta and gamma subunits of the IL-2 receptor without any affinity for CD25, and leads to significantly less toxicity than recombinant IL-2 in animal models.⁵ NL-201 triggers STAT5 phosphorylation with high potency, and leads to inflammatory cytokine signaling, tumor inhibition and prolonged survival in animal models. These studies suggest that NL-201 may provide antitumor benefit with an improved safety profile.

4.3 Justification for Dose

Part 1: NL-201 IV Monotherapy Dose Escalation

The FIH starting dose was selected based on evaluation of the totality of the nonclinical data including *in vitro* evaluation of PDn effects in human peripheral blood mononuclear cells (PBMCs), the most sensitive assay, and *in vivo* toxicity data in monkeys, the most sensitive species. The proposed starting dose of 0.1 µg/kg is predicted to result in an *in vivo* C_{max} in patients of approximately 2 ng/mL. The proposed dose is anticipated to approximate the lowest pharmacologically active dose (PAD) based on *in vitro* PDn evaluations and is 150- to 300-fold below the C_{max} achieved in monkeys given 11.44 µg/kg NL-201; a dose considered to be the NOAEL (see [Table 8](#) for dose escalation scheme).

Part 2: NL-201 Monotherapy Dose Expansion

The recommended monotherapy dose and schedule of NL-201 that is determined during dose escalation will be used during monotherapy dose expansion (Part 1). The DMC will determine this dose and schedule by considering the PK, PDn, tolerability, antitumor activity, and the occurrence of any cumulative toxicities over multiple cycles of NL-201. No randomization or dose escalation will occur, though dose reduction or delay for toxicity will be allowed.

Part 3: NL-201 in Combination with Pembrolizumab Dose Escalation

The planned dose of pembrolizumab for this study is 200 mg every 3 weeks (Q3W). Based on the totality of data generated in the Keytruda development program, 200 mg Q3W is an appropriate dose of pembrolizumab for adults across all indications. As outlined below, this dose is justified by:

- Clinical data from 8 randomized studies in melanoma and NSCLC indications demonstrating flat dose- and exposure-efficacy relationships from 2 mg/kg Q3W to 10 mg/kg every 2 weeks (Q2W) representing an approximate 5- to 7.5-fold exposure range (refer to the Investigator's Brochure)
- Population PK analysis showing that both fixed dosing and weight-based dosing provides similar control of PK variability with considerable overlap in the distributions of exposures, supporting suitability of 200 mg Q3W
- Clinical data showing meaningful improvement in benefit-risk including overall survival (OS) at 200 mg Q3W across multiple indications, and
- Pharmacology data showing full target saturation in both systemic circulation (inferred from PK data) and tumor (inferred from physiologically-based PK [PBPK] analysis) at 200 mg Q3W.

Among the 8 randomized dose-comparison studies, a total of 2262 participants were enrolled with melanoma and NSCLC, covering different disease settings (treatment naïve, previously treated, PD-L1 enriched, and all-comers) and different treatment settings (monotherapy and in combination with chemotherapy). Five studies compared 2 mg/kg Q3W versus 10 mg/kg Q2W (KN001 Cohort B2, KN001 Cohort D, KN002, KN010, and KN021), and 3 studies compared 10 mg/kg Q3W versus 10 mg/kg Q2W (KN001 Cohort B3, KN001 Cohort F2 and KN006). All of these studies demonstrated flat dose- and exposure-response relationships across the doses studied representing an approximate 5- to 7.5-fold difference in exposure. The 2 mg/kg (or 200 mg fixed-dose) Q3W provided similar responses to the highest doses studied. Subsequently, flat dose-exposure-response relationships were also observed in other tumor types including head and neck cancer, bladder cancer, gastric cancer and classical Hodgkin Lymphoma, confirming 200 mg Q3W as the appropriate dose independent of the tumor type. These findings are consistent with the mechanism of action of pembrolizumab, which acts by interaction with immune cells, and not via direct binding to cancer cells.

Additionally, pharmacology data clearly show target saturation at 200 mg Q3W. First, PK data in KN001 evaluating target-mediated drug disposition (TMDD) conclusively demonstrated saturation of PD-1 in systemic circulation at doses much lower than 200 mg Q3W. Second, a PBPK analysis was conducted to predict tumor PD-1 saturation over a wide range of tumor penetration and PD-1 expression. This evaluation concluded that pembrolizumab at 200 mg Q3W achieves full PD-1 saturation in both blood and tumor.

Finally, population PK analysis of pembrolizumab, which characterized the influence of body weight and other participant covariates on exposure, has shown that the fixed-dosing provides similar control of PK variability as weight-based dosing, with considerable overlap in the distribution of exposures from the 200 mg Q3W fixed dose and 2 mg/kg Q3W dose. Supported by these PK characteristics and given that fixed-dose has advantages of reduced dosing complexity and reduced potential of dosing errors, the 200 mg Q3W fixed-dose was selected for evaluation across all pembrolizumab protocols.

Part 4: NL-201 in Combination with Pembrolizumab Dose Expansion

The recommended dose and schedule of NL-201 in combination with pembrolizumab that is determined during dose escalation (Part 3) will be used during combination dose expansion. Supported by the mTPI design, the DMC will determine this dose and schedule by considering the PK, PDn, and any cumulative toxicities over multiple cycles of NL-201 in combination with pembrolizumab. No randomization or dose escalation will occur, though dose reduction or delay for toxicity will be allowed.

4.4 End of Study

End of Study (Individual Patient): A patient is considered to have completed the study if he/she has completed all phases of the study including the last visit shown in the Schedule of Events (Section 1.3; eg, last long-term follow up visit as described in Section 0).

Primary Completion: The primary completion date is defined as the date when the last patient is assessed or receives an intervention for the final collection of data to support the primary endpoint(s) for the purposes of conducting the primary analysis. This date is defined to be up to 30 days after the last patient has completed the last treatment.

End of Study: The end of the study is defined as the date of the last visit of the last patient in the study or last scheduled procedure shown in the Schedule of Events (Section 1.3) for the last patient in the study globally. The total study duration, including all follow-up, is expected to be approximately 5 years.

4.5 Patient Input on Study Design

Patient input was not obtained for this study.

5 STUDY POPULATION

Before any study-specific activities/procedures, the appropriate written informed consent must be obtained (see Section 10.1.3). Patients must meet all enrollment criteria to be eligible for this study.

Part 1 target population: Adult patients with measurable advanced and incurable solid tumors who have failed all lines of treatment, including CPIs if indicated.

Part 2 target population: Adult patients with pathologically proven diagnosis of the target disease indications, (1) malignant melanoma and (2) RCC, who have advanced and incurable disease and have failed at least 1 line of treatment, including CPIs.

Part 3 target population: Adult patients with histologically-confirmed solid tumors who have received ≥ 1 prior line of therapy for advanced or metastatic disease.

Part 4 target population: Adult patients with pathologically proven diagnosis of the target disease indications, (1) ICI naïve malignant melanoma and (2) ICI naïve RCC, and (3) patients with

NSCLC, melanoma, or HNSCC who have received prior treatment with pembrolizumab achieving a best response of SD.

5.1 Inclusion Criteria

Patients are eligible to be included in the study only if all of the following criteria apply at the time of screening:

1. Patients ≥ 18 years of age inclusive, at the time of signing the informed consent.
2. Capable of giving informed consent as described in [Section 10.1.3](#), which includes compliance with the requirements and restrictions listed in the informed consent form (ICF) and in this protocol.
3. Patients with measurable disease per RECIST 1.1 as assessed by the local site investigator/radiology. Lesions situated in a previously irradiated area are considered measurable if progression has been demonstrated in such lesions.
4. Patients with Eastern Cooperative Oncology Group (ECOG) performance status of 0 or 1.
5. Patients with adequate organ function, defined as:
 - a. Hematologic function laboratory values (specimens must be collected within 10 days prior to the start of study treatment):
 - i. Platelets $\geq 100,000/\text{mm}^3$
 - ii. Absolute neutrophil count (ANC) $> 1500/\text{mm}^3$
 - iii. Hemoglobin: Parts 1 and 2: ≥ 8.0 g/dL; Parts 3 and 4: ≥ 9.0 g/dL (NOTE: Criteria must be met without packed red blood cell transfusion within the prior 2 weeks. Participants can be on stable dose of erythropoietin (\geq approximately 3 months).
 - iv. Lymphocyte count $\geq 500/\text{mm}^3$
 - v. Eosinophils $< 1000/\text{mm}^3$
 - b. Renal function (specimens must be collected within 10 days prior to the start of study treatment): estimated glomerular filtration rate (eGFR) ≥ 50 mL/min/1.73 m² as determined by 2009 Chronic Kidney Disease Epidemiology Collaboration (CKD-EPI) equation,²⁹ or creatinine within normal limits (WNL)
 - c. Hepatic function (specimens must be collected within 10 days prior to the start of study treatment):
 - i. Aspartate aminotransferase (AST) and alanine aminotransferase (ALT): Parts 1 and 2: ≤ 3 x upper limit of normal (ULN), or ≤ 5 x ULN if known liver malignancy or metastasis; Parts 3 and 4: AST/ALT ≤ 2.5 x ULN, or ≤ 5 x ULN if known liver malignancy or metastasis
 - ii. Total bilirubin (TBL) WNL, or ≤ 3 x ULN if known Gilbert's syndrome
 - d. Adequate cardiovascular and respiratory function with transthoracic echocardiogram (ECHO) and pulmonary function testing showing no clinically significant findings. If ECHO is not available or appropriate according to the institutional standard, then multi-gated acquisition (MUGA) scan is permitted.

- e. Coagulation (specimens must be collected within 10 days prior to the start of study treatment): international normalized ratio (INR) OR prothrombin time (PT) $\leq 1.5 \times$ ULN unless participant is receiving anticoagulant therapy as long as PT or partial thromboplastin time (aPTT) is within therapeutic range of intended use of anticoagulants
6. At least 6 weeks from any prior nitrosurea or mitomycin C therapy; at least 4 weeks from any other prior chemotherapy or CPI; at least 2 weeks from any kinase inhibitor.
7. Women are not pregnant or breastfeeding and 1 of the following conditions applies:
 - a. Is a woman of non-childbearing potential as defined in [Section 10.4](#)
 - b. Is a woman of childbearing potential (WOCBP) and using a contraceptive method that is highly effective, with a failure rate of $< 1\%$ (as described in [Section 10.4](#)) during the study treatment period and for at least 60 days after the last dose of NL-201 (Parts 3 and 4 only: 120 days after the last dose of study treatment). The Investigator should evaluate the potential for contraceptive method failure (eg, noncompliance, recently initiated) in relationship to the first dose of study drug.
8. A WOCBP must have a negative highly sensitive pregnancy test (serum or urine) at screening.
9. Men are eligible to participate if they agree to the following during the study drug period and for at least 90 days after the last dose of NL-201 (Parts 3 and 4 only: 120 days after the last dose of pembrolizumab):
 - a. Refrain from donating sperm
 - b. For men with partners of childbearing potential or partners who are pregnant or breastfeeding: Use a male condom and should also be advised of the benefit for a female partner to use a highly effective method of contraception as a condom may break or leak when having sexual intercourse with a woman of childbearing potential who is not currently pregnant.

Part 1 Only

10. Patients with any relapsed or refractory advanced solid tumor, other than prostate cancer, who have progressed, not tolerated or are ineligible for all approved non-IL-2-based lines of therapy.

Parts 2 and 4 Only

11. Patients with a diagnosed target disease indication that has failed at least 1 line of systemic therapy.

Parts 3 and 4 Only

12. Part 3 only: Patients with histologically-confirmed solid tumors who have received ≥ 1 prior line of therapy for advanced or metastatic disease.
13. Part 4 only: Patients with a diagnosed target disease indication OR have received prior treatment with pembrolizumab achieving a best response of SD.
14. Part 4 only: Have archival tumor tissue sample available or newly obtained core/excisional biopsy of a tumor lesion not previously irradiated. Formalin-fixed, paraffin embedded (FFPE) tissue blocks are preferred to slides. If archival tissue is not available, and there is not a readily accessible lesion for biopsy, the biopsy may be waived with Sponsor approval.

Note: If submitting unstained cut slides, newly cut slides should be submitted to the testing laboratory within 14 days from the date slides are cut (details pertaining to tumor tissue submission can be found in the Procedures Manual).

Note: Archival biopsy should be within 5 years of screen date for PD-L1 analysis.

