2.2.1.2 Malignant Melanoma

Melanoma is 1 of the most common cancers in the United States, and is the most morbid malignancy of the skin, accounting for up to 75% of skin cancer-related deaths. While early melanoma is a localized disease, and is most often curable by surgical resection before metastatic spread, disseminated melanoma is a difficult disease to treat effectively.

Melanoma is a highly immunogenic tumor due to somatic mutations in the genomes of melanoma cells caused by ultraviolet radiation. These somatic mutations cause neoantigens in the tumor that can be recognized by the immune system, enabling a T-cell mediated antitumor immune response. Thus, immunotherapy can be an effective treatment for melanoma. Recent advances with CPIs have increased the 3-year survival rate of advanced melanoma to as high as 58%,³ but CR rates are generally low, and recurrent and refractory disease remains an unmet medical need. High-dose IL-2 can also potentiate T-cell mediated antitumor responses in melanoma, with an objective response rate (ORR) of 16%, including a CR rate of 6%.⁴ As described above, the severe toxicity associated with IL-2 therapy has limited its use to patients with good organ function who are being closely monitored by experienced clinicians in specialized medical centers.

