8.2.1 Assessment of Clinical Outcome: Imaging

Clinical outcome is measured with tumor assessment/response related endpoints as assessed according to RECIST 1.1,³⁰ and additionally, as assessed according to RECIST for use in cancer immunotherapy trials (iRECIST).³¹

At each tumor assessment visit, all images (as scheduled by the study protocol and additionally, all images as medically indicated) will be interpreted (assessment of response) by a radiologist according to RECIST 1.1 and additionally according to iRECIST. In Part 1, assessments will be performed locally. In Part 2, images must be sent to the central lab for assessment.

It is at the discretion of the treating Investigator whether to withdraw the patient from the study based on disease progression as determined by tumor assessment according to RECIST 1.1 or iRECIST or, in exceptional cases, based on clinical signs of progression.

Imaging for tumor response assessment is performed as indicated in the Schedule of Events ([Section 1.3](#)). During screening, baseline imaging by computed tomography (CT) of at least the chest, abdomen, and pelvis must be performed within 28 days prior to Cycle 1 Day 1. Radiologic evaluation of the brain is required for patients with history of CNS metastasis, or neurologic abnormality that suggests possible CNS metastasis or malignancy. Depending on the tumor entity, and if clinically indicated, imaging of further areas (eg, bone) should be conducted.

During the treatment period (and long-term follow-up in Parts 2 and 4 if study treatment was discontinued for reasons other than disease progression), CT of at least chest, abdomen, pelvis, and all areas affected with tumor lesions according to baseline imaging is performed. If clinically indicated, imaging of the brain and further areas should be conducted. Radiological imaging can also be done at additional times, if clinically indicated. All radiological images should be considered for tumor response assessment. If the patient cannot tolerate CT-contrast agents, assessments may be performed using magnetic resonance imaging (MRI). In a given patient, the same imaging modality and technique (eg, slice thickness, field of view) should be used for all scans during the study (if unable to use the same imaging modality and technique, the corresponding data will be excluded from the efficacy analysis).

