9.3 Populations for Analyses

For purposes of analysis, the following populations are defined in [Table 15](#).

Table 15 Populations for Analyses

Population	Description
Safety Evaluable Population	For Parts 1 and 2, all patients who receive any amount of study drug (NL-201) will be considered evaluable for safety regardless of the duration of NL-201 treatment. This population is defined for Part 1, and Part 2. For Parts 3 and 4, all patients who receive any amount of study drug (NL-201 or pembrolizumab) will be considered evaluable for safety regardless of the duration of treatment. This population is defined for Part 1 and Part 3, and Part 2 and Part 4, expansion cohorts. This population will be used to summarize safety parameters.
Efficacy Evaluable Population	For Parts 1 and 2, all patients with measurable disease by RECIST, who receive any amount of study drug (NL-201) or who discontinue study drug early due to disease progression and/or death will be considered evaluable for efficacy. For Parts 3 and 4, all patients with measurable disease by RECIST, who receive any amount of study drug (NL-201 or pembrolizumab) or who discontinue study drug early due to disease progression and/or death will be considered evaluable for efficacy. This population is defined for Part 1 and Part 3, and Part 2 and Part 4.
DLT-Evaluable Population	Patients enrolled into Part 1 or Part 3 who either complete the first 21 days of study or who experience a DLT.

DLT = dose limiting toxicity; RECIST = Response Evaluation Criteria in Solid Tumors

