9.4 Statistical Analyses

9.4.1 General Considerations

Demographic data and disease-related characteristics will be summarized separately for Part 1, by schedule (eg, IV Schedule A, IV Schedule B), and Part 2, by expansion cohort. Descriptive statistics (count and percent, mean, median, standard deviation, minimum, maximum) will be used. All patient data, efficacy and safety data will be summarized. Data from Parts 3 and 4 (NL-201 in combination with pembrolizumab) will be summarized in a similar manner.

A full Statistical Analysis Plan will be prepared to describe in full the statistical methods and analyses to be applied to the data arising in this study.

9.4.2 Determination of MTD in Part 1 and Part 3

For each schedule (IV Schedule A, IV Schedule B) in Part 1 (NL-201 monotherapy), the determination of MTD will be the highest dose for which the probability of a patient experiencing a DLT with NL-201 during Cycle 1 is $\leq 33\%$. Refer to [Section 9.2](#) for more details.

Similarly, for each schedule separately in Part 3 (NL-201 in combination with pembrolizumab), the determination of MTD will be the highest dose for which the probability of a patient experiencing a DLT with NL-201 during Cycle 1 is $\leq 33\%$. Refer to [Section 9.2](#) for more details.

9.4.3 Assessment of Preliminary Efficacy in Part 2 and Part 4

For NL-201 monotherapy, while tumor response data based on both RECIST 1.1 and iRECIST will be collected from all patients in dose escalation and expansion, formal analysis of tumor response will only be performed for the expansion cohorts in Part 2 based on iRECIST. Results will be presented and summarized using an exact 95% binomial confidence interval.

Other response-related efficacy parameters including time to response, duration of response, and clinical benefit rate will be also summarized by Part 2 expansion cohort.

In expansion cohorts in Part 2, OS and progression free survival (defined as the time from study entry to the time of disease progression or death from any cause) will be displayed graphically using Kaplan-Meier plots. Median PFS and OS will be extracted from the Kaplan-Meier plots along with their associated 95% confidence intervals. PFS and OS rates at 3 monthly intervals will also be extracted. Patients who do not experience progression or death will be censored at their last clinic visit contact for the assessment of disease progression.

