Cystic lesions: lesions that meet the criteria for radiographically defined simple cysts should not be considered as malignant lesions neither measurable nor non-measurable since they are, by definition, simple cysts. 'Cystic lesions' thought to represent cystic metastases can be considered as measurable lesions, if they meet the definition of measurability described above. However, if non-cystic lesions are present in the same patient, these are preferred for selection as target lesions.

Lesions that are situated in a previously irradiated area, or in an area patient to other loco-regional therapy, should be considered non-measurable lesions and will be evaluated only qualitatively as non-target lesions.

Baseline documentation of target and non-target lesions

When more than 1 measurable lesion is present at baseline all lesions up to a maximum of 5 lesions total (and a maximum of 2 lesions per organ) representative of all involved organs should be identified as target lesions and will be recorded and measured at baseline (this means in instances where patients have only 1 or 2 organ sites involved a maximum of 2 and 4 lesions respectively will be recorded).

Target lesions should be selected on the basis of their size (lesions with the longest diameter), be representative of all involved organs, but in addition should be those that lend themselves to reproducible repeated measurements.

Lymph nodes merit special mention since they are normal anatomical structures which may be visible by imaging even if not involved by tumor. As mentioned above pathological nodes which are defined as measurable and may be identified as target lesions must meet the criterion of a short axis of ≥ 15 mm by CT/MRI scan. Only the short axis of these nodes will contribute to the baseline sum. All other pathological nodes (those with short axis ≥ 10 mm but < 15 mm) should be considered non-target lesions. Nodes that have a short axis < 10 mm are considered non-pathological and should not be recorded or followed.

A sum of the diameters (longest for non-nodal lesions, short axis for nodal lesions) for all target lesions will be calculated and reported as the baseline sum diameters. If lymph nodes will be

included in the sum, only the short axis is added into the sum. The baseline sum diameters will be used as reference to further characterize any objective tumor regression in the measurable dimension of the disease.

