When the patient has only non-measurable disease: The same general concepts apply here as noted above, however, in this instance there is no measurable disease assessment to factor into the interpretation of an increase in non-measurable disease burden. Because worsening in non-target disease cannot be easily quantified (by definition: if all lesions are truly non-measurable) a useful test that can be applied when assessing patients for unequivocal progression is to consider if the increase in overall disease burden based on the change in non-measurable disease is comparable in magnitude to the increase that would be required to declare disease progression for measurable disease: ie, an increase in tumor burden representing an additional 73% increase in 'volume' (which is equivalent to a 20% increase diameter in a measurable lesion). Examples include an increase in a pleural effusion from 'trace' to 'large', an increase in lymphangitic disease from localized to widespread, or may be described as 'sufficient to require a change in therapy'. If 'unequivocal progression' is seen, the patient should be considered to have had overall disease progression at that point. While it would be ideal to have objective criteria to apply to non-measurable disease, the very nature of that disease makes it impossible to do so; therefore, the increase must be substantial.

Evaluation of overall lesion response according to RECIST 1.1

Only patients with at least 1 measurable lesion or non-measurable disease only at baseline (enrollment not allowed according to protocol) will be included in the tumor assessment according to RECIST 1.1. For patients with measurable disease at baseline the evaluation of overall response at each assessment is a composite of the target lesion response, non-target lesion response and presence of new lesions as shown below in **Table 18** (ie, target lesions with/without

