Non-iUPD/ PD	Non-iUPD/ PD	Yes	iUPD	Remains iUPD unless iCPD confirmed based on increase in size or number of new lesions previously identified

CR = complete response; iCPD = immune confirmed progressive disease; iCR = immune complete response; iPR = immune partial response; iRECIST = RECIST for use in cancer immunotherapy trials; iSD = immune stable disease; iUPD: immune unconfirmed progressive disease; NL = new lesion; NLNT = new lesion-non-target; NLT = new lesion-target; PD = progressive disease; PR = partial response; RECIST = Response Evaluation Criteria in Solid Tumors; SD = stable disease; SOM = sum of measures; TP = time point

- a Using RECIST 1.1 principles. If no pseudoprogression (PSPD) occurs, RECIST 1.1 and iRECIST categories for CR, PR and SD would be the same.
- b In any lesion category.
- c Previously identified in assessment immediately prior to this TP.

All patients will have their immune best overall response (iBOR) from the start of study treatment until the end of treatment classified as outlined in [Table 21](#).

Table 21 iRECIST Best Overall Response (iBOR)

TPR1	TPR2	TPR3	TPR4	TPR5	iBOR
iCR	iCR, iPR, iUPD, NE	iCR, iPR, iUPD, NE	iUPD	iUPD	iCR
iUPD	iPR, iSD, NE	iCR	iCR, iPR, iSD, iUPD, NE	iCR, iPR, iSD, iUPD, iCPD, NE	iCR
iUPD	iPR, iSD, NE	iPR, iSD, iUPD, NE	iPR, iSD, iUPD, NE, iCPD	iPR, iSD, iUPD, NE, iCPD	iPR
iUPD	iSD, NE	PR	iPR, iSD, iUPD, NE	iPR, iSD, iUPD, iCPD, NE	iPR
iUPD	iSD	iSD, iUPD, NE	iSD, iUPD, iCPD, NE	iSD, iUPD, iCPD, NE	iSD
iUPD	iCPD	Anything	Anything	Anything	iCPD
iUPD	iUPD	iCPD	Anything	Anything	iCPD
iUPD	NE	NE	NE	NE	iUPD

CR = complete response; iBOR = immune best overall response; iCPD = immune confirmed disease progression; iCR = immune complete response; iPR = immune partial response; iSD = immune stable disease; iUPD = immune unconfirmed progressive disease; NE = not evaluable that cycle; PD = progressive disease; PR = partial response; TPR = response at that time point

NOTES:

Table assumes a randomized study where confirmation of CR or PR is not required.

Designation "I" for BOR can be used to indicate prior iUPD to aid in data interpretation.

For patients with non-target disease only at baseline, only CR or non-CR/non-PD can be assigned at each TPR but is not shown in the table for ease of presentation.

Source: [Seymour 2017](#)³¹

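### Inclusion criterion 3 treats a progressing irradiated lesion as measurable; Section 10.6.2 treats every irradiated lesion as non-measurable and non-target, so a patient entered under one rule and scored under the other cannot reach PR or iPR

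*Combined protocol and SAP*

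**What the plan says.** - **Entry.** Section 5.1, criterion 3 requires measurable disease per RECIST 1.1, judged by the local investigator or radiology, and adds: "Lesions situated in a previously irradiated area are considered measurable if progression has been demonstrated in such lesions".
- **Scoring.** Section 10.6.2, under the categorization of tumor lesions, says: "Lesions that are situated in a previously irradiated area, or in an area patient to other loco-regional therapy, should be considered non-measurable lesions". The sentence goes on to have them evaluated only qualitatively, as non-target lesions. It makes no exception for progression.
- **Response categories.** Table 17 defines PR by a 30% fall in the sum of target-lesion diameters. Table 19, for patients with non-target lesions only, offers CR, Non-CR/Non-PD, NE and PD. For iRECIST, the notes to Table 21 (Section 10.6.3) say: "For patients with non-target disease only at baseline, only CR or non-CR/non-PD can be assigned at each TPR".
- **Enrolment and denominator.** Section 10.6.2 notes in passing that the protocol does not allow enrolment of patients with non-measurable disease only. The Efficacy Evaluable Population in Table 15 requires measurable disease by RECIST.
- **Analysis and readers.** Section 9.4.3: "formal analysis of tumor response will only be performed for the expansion cohorts in Part 2 based on iRECIST". Section 8.2.1: "In Part 2, images must be sent to the central lab for assessment". The same section sends the reader to Section 10.6 for lesion measurement and response.

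**The concern.** The two rules give opposite answers for the same lesion. For a patient whose only otherwise measurable disease is a progressing irradiated lesion, eligibility, the availability of PR or iPR, and membership of the efficacy denominator all depend on which section is followed. For a patient who has other target lesions too, the target-lesion sum depends on it.

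The damage comes from mixing the rules. In Part 2 the person who judges measurability at entry is local and the reader of response is central, so the two can work from different sections. Part 2 is the only part with a hypothesis test, and its formal response analysis is by iRECIST, so the missing iPR route bears on the tested quantity. A cohort stops at 0 responses in 18, so one lost partial response could end it. The Part 4 response-rate estimates inherit the same wording, but the documents do not say who reads Part 4 scans.

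**Working it through.** **1. The rules followed through for one patient** (only otherwise measurable disease: a progressing irradiated lesion)

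| Rule at entry | Rule at scoring | Result |
|---|---|---|
| 5.1 | 5.1 | Measurable; can be a target lesion; PR/iPR possible; in the efficacy population |
| 10.6.2 | 10.6.2 | No measurable disease; not to be enrolled; outside the efficacy population |
| 5.1 | 10.6.2 | Enrolled with no target lesion; Table 19 and the Table 21 note leave CR as the only response; denominator status undefined |

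Only the third row does harm. If Table 15 is read with criterion 3, the patient counts in the denominator and can respond only by CR, which lowers the response rate. If Table 15 is read with Section 10.6.2, the patient drops out of the denominator.

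Two places might have settled the conflict. The note in Section 10.6.2 about modifications to RECIST 1.1 concerns imaging methods only. Section 8.2.1 refers readers both to the RECIST publication and to Section 10.6 without saying which prevails.

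**2. Illustration of size for a Part 2 cohort**

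Inputs from Sections 9.1 and 9.2: null 2.5%, alternative 15%, 18 patients in stage 1, stop at 0/18, 30 in total. The protocol gives no final cutoff; success at 3 or more of 30 is assumed here.

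*Design with nobody affected.* Let X1 be responders among the first 18 and X2 among the next 12.

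Power = 1 − P(X1=0) − P(X1=1)·P(X2≤1) − P(X1=2)·P(X2=0)

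At 15%: 1 − 0.0536 − 0.1704 × 0.4435 − 0.2556 × 0.1422 = 0.834. The chance of stopping is 0.85^18 = 5.4%. The same calculation at 2.5% gives a type I error of 0.037. The protocol states 80% and 0.031, so the assumed cutoff with 18/30 does not reproduce its figures. That mismatch is a separate matter; here it means the baseline is not exactly the stated design.

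*With k affected patients of 30.* They fall into the two stages by the hypergeometric distribution; the others respond at 15%. Two cases:

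- Worst case: no CR, so affected patients respond at 0.
- CR only: Section 2.2.1.2 gives high-dose IL-2 in melanoma a 16% response rate with 6% CR, so CRs are 6/16 of responses and affected patients respond at 0.15 × 6/16 = 5.6%.

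Check for k = 1, worst case: the affected patient is in stage 1 with probability 18/30 (power 81.49%) or in stage 2 with probability 12/30 (power 81.97%). 0.6 × 81.49 + 0.4 × 81.97 = 81.7%.

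| Affected of 30 | Power, no CR | Stop at 0/18, no CR | Power, CR only | Stop at 0/18, CR only |
|---|---|---|---|---|
| 0 | 83.4% | 5.4% | 83.4% | 5.4% |
| 1 | 81.7% | 5.9% | 82.3% | 5.7% |
| 2 | 79.8% | 6.6% | 81.2% | 6.1% |
| 3 | 77.7% | 7.3% | 80.0% | 6.5% |
| 6 | 70.3% | 9.8% | 75.9% | 7.9% |

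The documents give no count of affected patients. One to three is an assumed plausible range and six is a stress case with no source.

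**The case against.** The best case for leaving this alone has four parts.

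- **A common source exists.** Criterion 3, Table 15 and the imaging section all cite RECIST, and readers are referred to its publication. Criterion 3 could be read as a specific exception to a general sentence in the appendix. But a general reference does not override an explicit sentence in the protocol's own scoring rules, and the protocol names no order of precedence.
- **The chain is narrow.** The patient must have no other measurable disease, the central reader must apply Section 10.6.2 literally, nobody must act on a baseline without target lesions, and the patient must stay in the denominator. This stands as a limit on frequency. The documents do not say which lesion rule the central lab uses, so mixing is inferred from the split of roles.
- **The size is unproven.** The cutoff is assumed, the number affected is unknown, and the 6/16 share comes from another drug in melanoma only. With one to three patients and that share, power stays at about 80% or above. This stands too, and is why the figures serve only as illustration.
- **Response is a secondary endpoint.** The primary endpoints are DLTs and safety, which are untouched. That lowers the severity but leaves the Part 2 test exposed.

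None of this removes the contradiction. A later analysis plan could settle the denominator but not enrolment decisions or baseline target selections already made.

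**Conclusion.** The concern holds. Sections 5.1 and 10.6.2 contradict each other on irradiated lesions that have progressed, and eligibility, target selection, access to PR or iPR and the Table 15 denominator turn on an unstated choice between them. The textual conflict is certain. Its effect on Part 2 is conditional on mixing the rules and probably modest: under the assumed cutoff, a loss of about 1 to 6 percentage points of power for one to three affected patients across the two cases, and a chance of stopping at 0/18 that rises from 5.4% to at most 7.3%. It should be corrected because it touches the tested endpoint and the correction is cheap.

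**What to change.** Use one measurability rule in Section 5.1, Section 10.6.2 and Table 15.

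1. Split the Section 10.6.2 sentence. (a) Lesions in a previously irradiated area are non-measurable unless progression in them was shown before baseline, in which case they are measurable and may be target lesions, as in criterion 3. (b) Lesions in areas given other loco-regional therapy stay non-measurable, as now.
2. State in Table 15 that measurable disease means measurable per criterion 3.
3. Give the rule to local and central readers before response reads begin in the expansion cohorts. For scans already read in dose escalation, record whether they will be re-read.

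Deleting the exception from criterion 3 would also remove the conflict, but it narrows eligibility.

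The cost is one split sentence, one phrase in Table 15 and one line of reader instructions, with the IRB/IEC approval that Section 10.1.1 requires for amendments; it can travel with the next one. No extra patients are needed, and no extra scans.
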